#### 3.6 Analysis cohorts

#### 3.6.1 Primary analysis cohort

ED patients with clinical sepsis, as identified by the combination of

- 1) Acute organ failure: SOFA score while in the ED  $\ge$ 2 points above baseline
- 2) Suspected or confirmed infection while in the ED, as identified by both:
  - c) Administration of ≥1 IV or IV-equivalent antibiotics while in the ED (see Appendix A)
  - d) Collection of  $\geq$ 1 body fluid cultures while in the ED

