#### 3.7.1 Primary outcome

Door-to-antibiotic time among all ED sepsis patients. Door-to-antibiotic time is the time from the first recorded arrival time in ED (usually ED triage or registration) and the time the first eligible antibiotic was administered (Appendix A).

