#### 3.7.2 Secondary outcomes

- Clinical/patient-centered secondary outcomes (measured among all ED sepsis patients):
  - 1) All-cause mortality to day 30
  - 2) All-cause mortality to 1 year
  - 3) In-hospital all-cause mortality
  - 4) Hospital charges: Amount charged to patient for their medical care during index ED visit and associated hospitalization.
  - 5) Hospital length of stay
- Process/feasibility secondary outcomes
  - 1) Code Sepsis activation rate: Measured as the percentage of all ED patients for whom the Code Sepsis protocol was activated.
  - 2) Code Sepsis activation accuracy metrics. Accurate Code Sepsis activation is defined as activation for patients who have sepsis while in the ED and no activation for patients who do not have sepsis in the ED.
- Adverse effects and unintended outcomes of protocol implementation

- 1) Antibiotic utilization percentage: measured as the fraction of (1) all ED patients; (2) Code Sepsis activation patients; or (3) "likely" sepsis patients who received IV or IV-equivalent antibiotics.
- 2) Antibiotic spectrum: Total Stenehjem antibiotic spectrum score for all antibiotics administered in first 24 hours, measured for (1) all ED patients or (2) sepsis patients
- 3) Antibiotic overtreatment rate: Percentage of "sepsis mimic" patients who received IV or IVequivalent antibiotics in the ED.
- 4) New onset C. difficile colitis incidence: Percentage of (1) all ED patients and (2) ED sepsis patients with a positive stool test for *Clostridium difficile* colitis between 72 hours and 90 days after ED arrival.
- 5) Adverse drug & allergic reaction incidence: Measured as the fraction of 1) all ED patients and (2) ED sepsis patients with a discharge diagnosis code consistent with anaphylaxis or with an adverse reaction to antibiotics (see Appendix C).
- Potential exploratory outcomes
  - 1) Measures of organ failure trajectory, to include change in the SOFA score between hospital day 1 and hospital day 3, and overall and organ-specific measures of organ failure-free days through day 28.

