# APPENDIX A — Eligible IV and IV-equivalent antibiotics

Antibiatia	Drond /altornative name	Eligible
Antibiotic	Brand/alternative name	routes
Acyclovir	Zovirax	IV
Amikacin	Amikin	IV
Amphotericin	Amphotec, Ambisome	IV
Ampicillin	Principen	IV
Ampicillin/sulbactam	Unasyn	IV
Anidulafungin	Eraxis	IV
Azithromycin	Zithromax, Zmax, Sumamed	IV
Aztreonam	Azactam	IV
Caspofungin	Cancidas	IV
Cefazolin	Ancef	IV
Cefdericol	Fetroja	IV
Cefepime	Maxipime	IV
Cefoperazone	Cefobid	IV
Cefotaxime	Claforan	IV
Cefotetan	Cefotan	IV
Cefoxitin	Mefoxin	IV
Ceftaroline	Teflaro	IV
Ceftazidime	Fortaz	IV
Ceftazidime/avibactam	Avycaz	IV
Ceftizoxime	Cefizox	IV
Ceftolozane/tazobactam	Zerbaxa, Ceftolozane	IV
Ceftriaxone	Rocephin	IV
Cefuroxime	Ceftin, Zinacef	IV
Chloramphenicol	Chloromycetin	IV
Cidofovir	Vistide	IV
Ciprofloxacin	Cipro, Ciprobay, Ciproxin	IV
Clindamycin	Cleocin	IV
Colistin	Colymycin	IV
Dalbavancin	Dalvance	IV
Daptomycin	Cubicin	IV
Delafloxacin	Baxdela	IV
Doripenem	Doribax	IV
Doxycycline	Doxychel, Vibramycin	IV
Eravacycline	Xerava	IV
Ertapenem	Invanz	IV
Erythromycin	Erythocin, Erythroped	IV
Fidaxomycin	Dificid	PO
Fluconazole	Diflucan	IV
Ganciclovir	Cytovene	IV
Gentamicin	Garamycin	IV
Imipenem/cilastin	Primaxin	IV
Isavuconazole	Cresemba, Isavuconazonium	IV
Itraconazole	Sporanox, Onmel	IV
Levofloxacin	Levaquin	IV
Linezolid	Ζγνοχ	IV

Antibiotic	Brand/alternative name	Eligible routes
Meropenem	Merrem	IV
Meropenem/vaborbactam	Vabomere	IV
Metronidazole	Flagyl	IV
Micafungin	Mycamine	IV
Minocycline	Minocin	IV
Moxifloxacin	Avelox	IV
Nafcillin	Unipen, Nallpen	IV
Ofloxacin	Floxin	IV
Omadadcycline	Nuzyra, Paratek	IV
Oritavancin	Orbactiv	IV
Oseltamavir	Tamiflu	PO
Oxacillin	Bastocillin	IV
Penicillin	Penicillin V, Pencillin G, Pen VK, Bicillin, Veetids, Pentids, Permapen, Pfizerpen,	IV
Peramavir	Rapivab	IV
Piperacillin/tazobactam	Zosyn	IV
Plazomicin	Zemdri	IV
Posaconazole	Noxafil	IV
Quinuopristin/dalfopristin	Synercid	IV
Remdesivir	Veklury	IV
Rifampin	Rifadin	IV
Telavancin	Vibativ	IV
Tetracycline	Achromycin, Tetracyn, Sumycin, Tetrachel	IV
Ticarcillin/clavulanate	Timentin	IV
Tidezolid	Sivextro	IV
Tigecycline	Tygacil	IV
Tobramycin		IV
Trimethoprim/sulfamethoxazole	Bactrim, Septra, Sulfatrim	IV
Vancomycin	Vancocin	PO
Vancomycin	Vancocin	IV
Voriconazole	Vfend	IV
Zanamivir	Relenza	IV

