# Inclusion/exclusion criteria

Cohort	Inclusion	Exclusion	Cohort eligibility indicator variable*
ED sepsis cohort (primary analysis cohort)	
 
(1) Age ≥18 years
 
(2) Arrival to an intervention or control ED during study period
 
(3) Met all Sepsis-3 criteria in the ED
 
Acute organ failure in the ED defined by SOFA score while in the ED ,≥2 points above baseline
 
Suspected or confirmed infection while in the ED, based on having both: 
 
i. Administration of ,≥1 IV or IV-equivalent antibiotics while in the ED for suspected infection (i.e. antibiotics not given for prophylaxis)
 
ii. Collection of ,≥1 body fluid cultures while in the ED
 
 
 
	
 
Trauma patient
 
Subsequent eligible ED visit with sepsis after first eligible encounter during an analysis window
 
	cohort_sepsis
All adult ED patients cohort	
 
(1) Age ≥18 years
 
(2) Arrival to an intervention or control ED during study period
 
	
 
Trauma patient
 
Received antibiotics within 6 hours prior to study ED arrival
 
Subsequent eligible ED visit after first eligible encounter during an analysis window
 
Left ED without evaluation or treatment
 
	cohort_all
Sepsis high-risk cohort	
 
Age ≥18 years
 
Arrival to an intervention or control ED during study period
 
First recorded temperature ≥38.0°C
 
First-recorded vital sign data meets ≥2 of:         
 
a. Systolic blood pressure <90 mmHg
 
b. Glasgow Coma Scale (GCS) score <15
 
c. Respiratory rate ≥22 breaths/min or oxygen saturation <85%
 
 
 
	
 
Trauma patient
 
Received antibiotics within 6 hours prior to study ED arrival
 
Subsequent eligible ED visit after first eligible encounter during an analysis window
 
Left ED without evaluation or treatment
 
	cohort_risk

Cohort	Inclusion	Exclusion	Cohort eligibility indicator variable*
Sepsis	(1) Age ≥18 years	(1) Trauma patient	cohort_mimics
mimic	(2) Arrival to an intervention or control ED during study period	(2) Received antibiotics	

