### **Outcomes & analyses**

Primary outcome

	Analysis		Outcome
Outcome	cohort	Description	variable
Door-to-antibiotic time	Sepsis cohort	Time (minutes) from ED arrival to administration of first IV (or equivalent) antimicrobial while in the ED	abx_elapsed

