### Safety outcomes

	Analysis		
Outcome	cohort	Description	Outcome variable
Antibiotic utilization	All patient	Receipt of IV or equivalent antibiotics within 24	abx_24h
	cohort	hours of ED arrival	
Antibiotic utilization	Sepsis	Receipt of of receiving IV or equivalent antibiotics	abx_24h
	high-risk	within 24 hours of ED arrival	
	cohort		
Potential adverse effect	Sepsis	Antibiotic-related adverse event (a discharge	<pre>icd10_ae_summary</pre>
of antibiotics	cohort	diagnosis code consistent with anaphylaxis or	
		with an adverse reaction to antibiotics)	
Potential adverse effect	All patient	Antibiotic-related adverse event (a discharge	<pre>icd10_ae_summary</pre>
of antibiotics	cohort	diagnosis code consistent with anaphylaxis or	
		with an adverse reaction to antibiotics)	
New-onset C difficile	Sepsis	New positive stool test for Clostridium difficile	cdiff_72h_new_analysis
	cohort*	colitis between 72 hours and 90 days after ED	ineligible)
		arrival	
		* Excludes patients with a positive C. difficile	
		assay in the 14 days preceding ED arrival or	
		within 72 hours following ED arrival	

	Analysis		
Outcome	cohort	Description	Outcome variable
New-onset C difficile	All patient cohort*	New positive stool test for Clostridium difficile colitis between 72 hours and 90 days after ED arrival	cdiff_72h_new_analysis (missing if ineligible)
		* Excludes patients with a positive C. difficile assay in the 14 days preceding ED arrival or within 72 hours following ED arrival	
Antibiotic	Sepsis	Receipt of antibiotics in the ED among ED	abx_ed
overtreatment rate	mimic	patients with a primary hospital discharge	
	cohort	diagnosis of congestive heart failure or venous	
		thromboembolism	
False-positive	Sepsis	Final adjudicated infection status is "not	uninfected
presumptive infection	cohort	infected" among ED patients meeting sepsis	
diagnosis rate		criteria	

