Antibiotic spectrum	Sepsis cohort*	Total antibiotic spectrum score for all IV or equivalent antibiotics administered in first 24 hours using antibiotic spectrum scoring system developed by Stenehjem et al. (Clin Infect Dis 2016;63:1273-1280). Individual antibiotics have spectrum scores of 1 to 5, with the total score resulting from summation of the spectrum scores for each unique antibiotic administered during the first 24 hours. Minimum total 24-hour score is therefore 1 (administration of a single, minimum-spectrum antibiotic), with no maximum score.	abx_24h_score_total (missing if ineligible)
		* Patients receiving no antibiotics (only antivirals or antifungals) are excluded from analysis.	

	Analysis		
Outcome	cohort	Description	Outcome variable
Antibiotic spectrum	All patient cohort receiving antibiotics*	Total antibiotic spectrum score for all antibiotics administered in first 24 hours using antibiotic spectrum scoring system developed by Stenehjem et al. (Clin Infect Dis 2016;63:1273- 1280). Individual antibiotics have spectrum scores of 1 to 5, with the total score resulting from summation of the spectrum scores for each unique antibiotic administered during the first 24 hours. Minimum total 24-hour score is therefore 1 (administration of a single, minimum-spectrum antibiotic), with no maximum score.	abx_24h_score_total (missing if ineligible)
		* Patients receiving no antibiotics (only antivirals or antifungals) are excluded from analysis.	
Antibiotic spectrum	Sepsis high-risk patients treated with antibiotics*	Total antibiotic spectrum score for all antibiotics administered in first 24 hours using antibiotic spectrum scoring system developed by Stenehjem et al. (Clin Infect Dis 2016;63:1273- 1280). Individual antibiotics have spectrum scores of 1 to 5, with the total score resulting from summation of the spectrum scores for each unique antibiotic administered during the first 24 hours. Minimum total 24-hour score is therefore 1 (administration of a single, minimum-spectrum antibiotic), with no maximum score.	abx_24h_score_total (missing if ineligible)
		or antifungals) are excluded from analysis.	

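### Antivirals and antifungals can admit patients to the sepsis cohort, stop the door-to-antibiotic clock and count as antibiotic use, and no antibacterial-only analysis is planned

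*SAP*

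**What the plan says.** **Cohort entry.** Protocol 3.6.1 requires "Administration of ≥1 IV or IV-equivalent antibiotics while in the ED (see Appendix A"), plus a body fluid culture and a SOFA score at least 2 points above baseline. The SAP (Inclusion/exclusion criteria) narrows this only by indication: "IV-equivalent antibiotics while in the ED for suspected infection (i.e. antibiotics not given for prophylaxis"). It does not restrict drug class.

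**Clock.** Protocol 3.7.1 stops it at "the time the first eligible antibiotic was administered (Appendix A"). The SAP primary outcome says "administration of first IV (or equivalent) antimicrobial while in the ED", and its secondary outcome of 3 hours or less uses the same event.

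**Drug list.** Appendix A is headed "Eligible IV and IV-equivalent antibiotics". It includes acyclovir, cidofovir, ganciclovir, oral oseltamivir, peramivir, remdesivir and zanamivir, and nine antifungals (amphotericin, three echinocandins and five azoles).

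**Utilization and overtreatment.** Protocol 3.7.2 uses the Appendix A term for both; overtreatment, for example, is the percentage of sepsis mimic "patients who received IV or IVequivalent antibiotics in the ED". The SAP defines abx_24h as "Receipt of IV or equivalent antibiotics within 24" hours of ED arrival and abx_ed as receipt of antibiotics in the ED. It attaches no drug list to either.

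**Spectrum score.** Here the SAP adds: "Patients receiving no antibiotics (only antivirals or antifungals) are excluded from analysis". The footnote is attached to the sepsis cohort as well as to the wider cohorts.

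**COVID-related adjustment.** SARS-CoV-2 test result appears only among the propensity-score covariates (SAP, Data analysis). The weighting is used only if the parallel-trends pre-test fails. The covariate lists for the primary/secondary models and for the safety models omit it. No sensitivity analysis is restricted to antibacterials.

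**The concern.** The trial's rationale is delay to antibiotics (Protocol 3.1), and its mechanism is an antibiotic pack brought to the bedside, with regimens chosen partly on local resistance patterns (Protocol 5.2). Antiviral timing is not what that mechanism targets. Yet a patient given oral oseltamivir at 30 minutes and a first antibacterial at 200 minutes scores 30. A patient with viral pneumonia, a culture drawn and only remdesivir given joins the cohort with a time that may reflect when a test result came back.

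The pre phase ended in November 2019, and the post phase began in February 2020. If antiviral prescribing changed by different amounts at the intervention and control EDs, that difference would be read as an effect of Code Sepsis on door-to-antibiotic time. In abx_24h it would be read as a change in antibiotic use. That variable is more exposed than the ED-only ones, because its 24-hour window can run past the ED stay into the admission.

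**Working it through.** **1. Does the drug list matter for cohort and clock?** Appendix A has 76 rows, of which 7 + 9 = 16 (21%) are antiviral or antifungal. This is a share of the list, not of prescribing. The spectrum footnote excludes sepsis-cohort members who had only antivirals or antifungals. Cohort entry requires an eligible drug, so those members can have entered only through an antiviral or antifungal. The plan therefore expects such patients.

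**2. Precision of the primary estimate.** Inputs from the Protocol (7.3) and SAP (Power): SD 75 minutes; 1,650 intervention and 2,200 control sepsis patients per year; one-year phases.
- SE = 75 × √(2/1650 + 2/2200) = 3.45 minutes.
- Two-sided power for 16 minutes = Φ(16/3.45 − 1.96) = 99.6%. The 90%-power detectable change is 3.24 × 3.45 = 11.2 minutes.
- The stated 90% at 16 minutes is not reproduced this way. It implies an SE of 16/3.24 = 4.94 minutes. The plan used simulations whose details are not shown, and its figure is the more conservative one, so this is not evidence of an error. Both SEs are used below.

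**3. Shift in the interaction coefficient.** If antivirals or antifungals precede the first antibacterial by the same lead at all sites, the shift on the additive scale is

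(change in antiviral- or antifungal-first share at the intervention ED − the same change at the control EDs) × lead in minutes.

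The documents give neither quantity, so both are assumptions:

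| Differential share | Lead 60 min | Lead 100 min |
|---|---|---|
| 1 point | 0.6 min | 1.0 min |
| 5 points | 3.0 min | 5.0 min |
| 10 points | 6.0 min | 10.0 min |

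The chance of a nominally significant result with no true effect, nominally 5%, then becomes:

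| Shift | SE 3.45 | SE 4.94 |
|---|---|---|
| 0.6 min | 5.3% | 5.2% |
| 3 min | 14% | 9% |
| 5 min | 30% | 17% |
| 10 min | 83% | 53% |

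A shift of the full 16 minutes needs a differential share of 16/60 = 27 points or 16/100 = 16 points. An equal change at all sites gives zero.

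**4. Direction.** Early antivirals shorten the recorded time. Patients who enter the cohort only through a late antiviral lengthen the mean. The sign depends on the mix.

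**5. Would the plan detect or remove it?** The parallel-trends test uses pre-implementation data only, so it cannot see a shift that arises in the post phase. If it passes, no weighting is applied and SARS-CoV-2 status is not in the model. The main model does adjust for temperature, acute physiology score, SOFA and infection source, which may absorb part of a change in case mix. It cannot correct a clock stopped by another drug class.

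**6. Utilization (abx_24h, all-patient cohort).** Annual visits from Protocol Table 1: 89,000 intervention; 49,000 + 65,000 = 114,000 control. Assume 10% use.
- SE = √[0.1 × 0.9 × 2 × (1/89,000 + 1/114,000)] = 0.19 points. An assumed differential of 0.5 points (0.005 × 89,000 = 445 visits) is 2.6 SE.
- Those counts are gross. The SAP cohort drops minors, trauma, repeat visits, recent antibiotics and patients who left unevaluated. If half the visits remain (assumption), SE is 0.27 points and the ratio 1.9, short of nominal significance.

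**7. Overtreatment (abx_ed, mimic cohort).** Any infection code in any position removes the patient. The infection code list is not in the documents. Assuming that it covers COVID-19 and influenza, only empirical antivirals in patients with no infection code could count.

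**The case against.** The broad list is a prespecified choice and can be defended. Protocol 1.2 defines sepsis by infection of any kind and lets a positive molecular test support suspected infection. The clock follows the same list as cohort entry. An antibacterial-only primary would drop viral and fungal sepsis and so change the estimand. It would also keep COVID patients given empirical antibacterials, so it would not remove every change in case mix. This stands, and it is why the primary should not be replaced. It does not explain why the narrower version is left unplanned.

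The control EDs remove changes common to all sites, and small differentials matter little. This also stands. With one intervention ED and two control EDs, however, an equal change is an assumption, and nothing in the plan checks it.

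Three stronger readings are tempting, and the documents do not support them:
- *That COVID-era antivirals would inflate the overtreatment rate.* The rule against any infection code largely protects it.
- *That the SAP contradicts itself.* The spectrum score starts at 1 for a single antibiotic, so a patient with no antibiotic has no valid value. The footnote is a scoring necessity. What it shows is that the word carries two meanings.
- *That the SAP's abx_24h and abx_ed certainly count antivirals.* The Protocol's definitions do. The SAP says antibiotics there and antimicrobial for the primary, and its footnote uses the narrow sense, so its wording is ambiguous.

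The SAP also treats the safety outcomes as hypothesis generating, so an error there would not become a confirmatory claim.

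**Conclusion.** The point holds for the sepsis cohort criterion, the primary outcome and the outcome of 3 hours or less, and under the Protocol's definition for antibiotic utilization. A change in antiviral or antifungal use that differs between the intervention and control EDs would enter the interaction coefficient and abx_24h with no change in antibacterial care, and the main models have no safeguard against it.

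Size and direction are unknown. Under the assumed 1 to 10 points and 60 to 100 minutes, the shift is 0.6 to 10 minutes: negligible at the low end and a serious fraction of the 16-minute target at the high end. It is zero on the additive scale if the change is equal at all sites. A reader might infer that the primary result would be invalid. The documents do not show that; they show that the published result could not be separated from this explanation without an extra analysis. The overtreatment rate is largely outside the problem. This should be fixed, but it does not undermine the design.

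**What to change.** 1. Keep the Protocol-defined cohort and primary outcome.
2. Flag each Appendix A drug as antibacterial, antiviral or antifungal, and state which classes count for each variable.
3. Prespecify, as a key sensitivity analysis, an antibacterial-only version of the cohort antibiotic criterion, abx_elapsed and abx_lt3h.
4. Define abx_24h and abx_ed by antibacterials only, matching the spectrum score, with the all-antimicrobial version as a sensitivity analysis.
5. Report the share of sepsis patients whose first listed drug was an antiviral or antifungal, by site and phase. This shows directly whether a differential change occurred.

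The cost is a drug-class flag on administration data already collected (Protocol 6.5), an amended SAP text and one additional analysis. Patients given only antivirals or antifungals, probably few, are absent from the antibacterial-only analyses but stay in the primary.

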# Secondary outcomes

	Analysis		Outcome
Outcome	cohort	Description	variable
Door-to-antibiotic time	Sepsis	Time (minutes) from ED arrival to administration	abx_lt3h
≤3 hours	cohort	of first IV (or equivalent) antimicrobial while in	
		the ED less than or equal to 180 minutes	
30-day mortality	Sepsis	Key clinical/secondary outcome	mort_30d
	cohort		
1-year mortality	Sepsis		mort_1y
	cohort		
In-hospital mortality	Sepsis		mort_hosp
	cohort		
Hospital charges	Sepsis		hosp_charges
	cohort		
Hosp. length of stay (days)	Sepsis		los_hosp
	cohort		

### Safety outcomes

	Analysis		
Outcome	cohort	Description	Outcome variable
Antibiotic utilization	All patient	Receipt of IV or equivalent antibiotics within 24	abx_24h
	cohort	hours of ED arrival	
Antibiotic utilization	Sepsis	Receipt of of receiving IV or equivalent antibiotics	abx_24h
	high-risk	within 24 hours of ED arrival	
	cohort		
Potential adverse effect	Sepsis	Antibiotic-related adverse event (a discharge	<pre>icd10_ae_summary</pre>
of antibiotics	cohort	diagnosis code consistent with anaphylaxis or	
		with an adverse reaction to antibiotics)	
Potential adverse effect	All patient	Antibiotic-related adverse event (a discharge	<pre>icd10_ae_summary</pre>
of antibiotics	cohort	diagnosis code consistent with anaphylaxis or	
		with an adverse reaction to antibiotics)	
New-onset C difficile	Sepsis	New positive stool test for Clostridium difficile	cdiff_72h_new_analysis
	cohort*	colitis between 72 hours and 90 days after ED	ineligible)
		arrival	
		* Excludes patients with a positive C. difficile	
		assay in the 14 days preceding ED arrival or	
		within 72 hours following ED arrival	

	Analysis		
Outcome	cohort	Description	Outcome variable
New-onset C difficile	All patient cohort*	New positive stool test for Clostridium difficile colitis between 72 hours and 90 days after ED arrival	cdiff_72h_new_analysis (missing if ineligible)
		* Excludes patients with a positive C. difficile assay in the 14 days preceding ED arrival or within 72 hours following ED arrival	
Antibiotic	Sepsis	Receipt of antibiotics in the ED among ED	abx_ed
overtreatment rate	mimic	patients with a primary hospital discharge	
	cohort	diagnosis of congestive heart failure or venous	
		thromboembolism	
False-positive	Sepsis	Final adjudicated infection status is "not	uninfected
presumptive infection	cohort	infected" among ED patients meeting sepsis	
diagnosis rate		criteria	
Antibiotic spectrum	Sepsis cohort*	Total antibiotic spectrum score for all IV or equivalent antibiotics administered in first 24 hours using antibiotic spectrum scoring system developed by Stenehjem et al. (Clin Infect Dis 2016;63:1273-1280). Individual antibiotics have spectrum scores of 1 to 5, with the total score resulting from summation of the spectrum scores for each unique antibiotic administered during the first 24 hours. Minimum total 24-hour score is therefore 1 (administration of a single, minimum-spectrum antibiotic), with no maximum score.	abx_24h_score_total (missing if ineligible)
		* Patients receiving no antibiotics (only antivirals or antifungals) are excluded from analysis.	

	Analysis		
Outcome	cohort	Description	Outcome variable
Antibiotic spectrum	All patient cohort receiving antibiotics*	Total antibiotic spectrum score for all antibiotics administered in first 24 hours using antibiotic spectrum scoring system developed by Stenehjem et al. (Clin Infect Dis 2016;63:1273- 1280). Individual antibiotics have spectrum scores of 1 to 5, with the total score resulting from summation of the spectrum scores for each unique antibiotic administered during the first 24 hours. Minimum total 24-hour score is therefore 1 (administration of a single, minimum-spectrum antibiotic), with no maximum score.	abx_24h_score_total (missing if ineligible)
		* Patients receiving no antibiotics (only antivirals or antifungals) are excluded from analysis.	
Antibiotic spectrum	Sepsis high-risk patients treated with antibiotics*	Total antibiotic spectrum score for all antibiotics administered in first 24 hours using antibiotic spectrum scoring system developed by Stenehjem et al. (Clin Infect Dis 2016;63:1273- 1280). Individual antibiotics have spectrum scores of 1 to 5, with the total score resulting from summation of the spectrum scores for each unique antibiotic administered during the first 24 hours. Minimum total 24-hour score is therefore 1 (administration of a single, minimum-spectrum antibiotic), with no maximum score.	abx_24h_score_total (missing if ineligible)
		or antifungals) are excluded from analysis.	

